Malignancies	
Malignancy is defined using PTs from the Malignant or unspecified tumors SMQ as specified in MedDRA (SMQ: 20000091, which includes the sub-SMQs:
 
 
• 20000194 [Malignant tumours], including sub-SMQs of 20000227 [Haematological malignant tumours] and 20000228 [Non-haematological malignant tumours]
 
• 20000195 [Tumours of unspecified malignancy], including sub-SMQs of 20000229 [Haematological tumours of unspecified malignancy] and 20000230 [Non-haematological tumours of unspecified malignancy]
 
• Nonmelanoma Skin Cancer (NMSC) 
 
○ Basal Cell Carcinoma, PTs include: 
 
▪ Basal cell carcinoma
 
▪ Basosquamous carcinoma
 
▪ Basosquamous carcinoma of skin
 
 
 
○ Squamous Cell Carcinoma, PTs include: 
 
▪ Squamous cell carcinoma of skin
 
▪ Bowen’s disease
 
▪ Lip squamous cell carcinoma
 
 
 
 
 
	
Fisher’s exact test for Safety Population and summary for IR Population: TEAE by PT within category
 
Listing: TEAE (to be prepared in Spotfire)

Special Safety Topic	Definition / Derivation	Analysis / Summary / Listing
	
 
▪ Skin squamous cell carcinoma metastatic
 
▪ Keratoacanthoma
 
• Malignancies excluding NMSC: all PTs in the Malignant or unspecified tumors SMQ excluding the 8 defined NMSC PTs.
 
	
Depressions	
Depression is defined using the PTs from the Depression and suicide/self-injury SMQ as specified in MedDRA (SMQ: 20000035, which includes the sub-SMQs: 20000037 [Suicide/self-injury] and 20000167 [Depression (excl suicide and self-injury)]).
	
Fisher’s exact test for Safety Population and summary for IR Population: TEAE by PT within SMQ and sub-SMQ Listing: TEAE (to be prepared in Spotfire)

Inflammatory Bowel Disease (IBD)	
IBD will be identified using the following subcategory and MedDRA PTs. The narrow terms are considered IBD.
 
IBD (Narrow terms)
 
 
• Inflammatory Bowel Disease: Inflammatory bowel disease
 
• Crohn’s Disease: Crohn’s disease
 
• Ulcerative Colitis: Acute haemorrhagic ulcerative colitis; Colitis ulcerative; Proctitis ulcerative
 
 
Non-Specific Terms (Events That Can Occur with IBD (Broad Terms)): The PTs in this category are listed in Appendix 10.
	
Fisher’s exact test for Safety Population in Period 2 and Period between Week 0 and Week 16 and summary for IR Population: TEAE by PT within subcategory Number and percentage of patients, as well as the exposure-adjusted incidence rates will be presented for the Safety Population and IR Population in Period 2. Listing: TEAE (to be prepared in Spotfire)

Interstitial Lung Disease (ILD)	
ILD is defined using the following terms:
 
 
• Broad and narrow terms in the Interstitial lung disease SMQ (20000042)
 
• Additional 6 PTs from Eosinophilic pneumonia SMQ (20000157):                             
 
○ Angiolymphoid hyperplasia with eosinophilia (Narrow)
 
○ Eosinophilic bronchitis (Narrow)
 
 
 
	
Listing: TEAE (to be prepared in Spotfire)

Special Safety Topic	Definition / Derivation	Analysis / Summary / Listing
	
 
○ Hypereosinophilic syndrome (Narrow)
 
○ Loeffler’s syndrome (Narrow)
 
○ Pulmonary eosinophilia (Narrow)
 
○ Pulmonary vasculitis (Narrow)
 
	

Abbreviations: AE = adverse event; ALP = alkaline phosphatase; eCRF = electronic case report form; GGT = gamma-glutamyl transferase; HLT = high-level term; IR = inadequate responder; PT = preferred term; SAE = serious adverse event; SMQ = standardized MedDRA Query; TEAE = treatment emergent adverse event; ULN = upper limit of normal.

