### 7.1. Discontinuation from Study Treatment

#### 7.1.1. *Permanent Discontinuation from Study Treatment*

The following criteria must be followed for discontinuation from study treatment.

- [1] Discontinuation of the investigational product for abnormal liver tests should be considered by the investigator when a patient meets 1 of the following conditions after consultation with the Lilly designated medical monitor:
  - ALT or AST >8 times ULN
  - ALT or AST >5 times ULN for more than 2 weeks
  - ALT or AST >3X ULN and total bilirubin level >2 times ULN or prothrombin time >1.5 times ULN
  - ALT or AST >3 times ULN with the appearance of fatigue, nausea, vomiting, right upper-quadrant pain or tenderness, fever, rash, and/or eosinophilia (>5%)
  - alkaline phosphatase >2.5 times ULN and total bilirubin >2 times ULN
  - alkaline phosphatase >2.5 times ULN with the appearance of fatigue, nausea, vomiting, right upper quadrant pain or tenderness, fever, rash, and/or eosinophilia (>5%)
- [2] Other laboratory tests (**Note:** Laboratory test(s) that may result in discontinuation based on a single result may be repeated only once if there is a technical error or clinical reason to believe a result may need to be retested. Laboratory tests can only be repeated after consultation with Lilly medical. Investigational product should not be administered in these cases until retest result is available.):

- Neutrophil (segmented) counts (see safety monitoring for neutropenia in Section 8.4.10.1):
    - $<500$  cells/ $\mu\text{L}$  ( $<0.50 \times 10^3/\mu\text{L}$  or  $<0.50$  GI/L)
    - $\geq 500$  and  $<1000$  cells/ $\mu\text{L}$  ( $\geq 0.50 \times 10^3/\mu\text{L}$  and  $<1.00 \times 10^3/\mu\text{L}$  or  $\geq 0.50$  GI/L and  $<1.00$  GI/L) (based on 2 test results; the second test performed within 1 week from knowledge of the initial result)
    - $\geq 1000$  and  $<1500$  cells/ $\mu\text{L}$  ( $\geq 1.00 \times 10^3/\mu\text{L}$  and  $<1.50 \times 10^3/\mu\text{L}$  or  $\geq 1.00$  GI/L and  $<1.50$  GI/L) (based on 3 test results as specified in Section 8.4.10.1)
      - AND - a concurrent infection
  - Total WBC count  $<2000$  cells/ $\mu\text{L}$  ( $<2.00 \times 10^3/\mu\text{L}$  or  $<2.00$  GI/L)
  - Lymphocyte count  $<500$  cells/ $\mu\text{L}$  ( $<0.50 \times 10^3/\mu\text{L}$  or  $<0.50$  GI/L)
  - Platelet count  $<50,000$  cells/ $\mu\text{L}$  ( $<50 \times 10^3/\mu\text{L}$  or  $<50$  GI/L)

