#### **8.4.10. Safety Monitoring**

Lilly will periodically review evolving aggregate safety data within the study by appropriate methods.

If a study patient experiences elevated ALT  $\geq 3$ xULN, alkaline phosphatase  $\geq 2$ xULN, or elevated total bilirubin  $\geq 2$ xULN, clinical and laboratory monitoring is to be initiated by the investigator. Details for hepatic monitoring depend upon the severity and persistence of observed laboratory test abnormalities. For other AESIs or abnormal lab results, please refer to the appropriate protocol section that addresses these topics. To ensure patient safety and comply with regulatory guidance, the investigator is to consult with the Lilly clinical research physician/clinical research scientist regarding collection of specific recommended clinical information and follow-up laboratory tests. See [Appendix 4](#).

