	
Elevations in hepatic laboratory tests (ALT, AST, ALP, total bilirubin) using Performing Lab Reference Ranges are defined as:
 
 
• Include scheduled visits, unscheduled visits, and repeat measurements.
 
• Alanine aminotransferase (ALT) or aspartate aminotransferase (AST): maximum postbaseline measurement <math>\geq 3</math> times (<math>3\times</math>), 5 times (<math>5\times</math>), 10 times (<math>10\times</math>), and 20 times (<math>20\times</math>) the Performing Lab upper limit of normal (ULN) for all patients with a postbaseline value. 
 
○ The analysis of <math>3\times</math> ULN will contain 4 subsets: patients whose non-missing maximum baseline value is <math>\leq 1\times</math> ULN, <math>>1\times</math> ULN to <math><3\times</math> ULN, <math>\geq 3\times</math> ULN, or missing.
 
○ The analysis of <math>5\times</math> ULN will contain 5 subsets: patients whose non-missing maximum baseline value is <math>\leq 1\times</math> ULN, <math>>1\times</math> ULN to <math><3\times</math> ULN, <math>\geq 3\times</math> ULN to <math><5\times</math> ULN, <math>\geq 5\times</math> ULN, or missing.
 
○ The analysis of <math>10\times</math> ULN will contain 6 subsets: patients whose non-missing maximum baseline value is <math>\leq 1\times</math> ULN, <math>>1\times</math> ULN to <math><3\times</math> ULN, <math>\geq 3\times</math> ULN to <math><5\times</math> ULN, <math>\geq 5\times</math> ULN to <math><10\times</math> ULN, <math>\geq 10\times</math> ULN, or missing.
 
○ The analysis of <math>20\times</math> ULN will contain 7 subsets: patients whose non-missing maximum baseline value is <math>\leq 1\times</math> ULN, <math>>1\times</math> ULN to <math><3\times</math> ULN, <math>\geq 3\times</math> ULN to <math><5\times</math> ULN, <math>\geq 5\times</math> ULN to <math><10\times</math> ULN, <math>\geq 10\times</math> ULN to <math><20\times</math> ULN, <math>\geq 20\times</math> ULN, or missing.
 
 
 
	
Fisher’s exact test for Safety Population and summary for IR Population: Elevations in hepatic laboratory tests: maximum baseline category to abnormal maximum postbaseline category

Special Safety Topic	Definition / Derivation	Analysis / Summary / Listing

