	
Shift for ALT, AST, and total bilirubin from maximum baseline to maximum postbaseline will be produced with the requirements using Performing Lab Reference Ranges:
 
 
• Include scheduled visits, unscheduled visits, and repeat measurements.
 
• Use the maximum non-missing value in the baseline period.
 
• Use the maximum non-missing postbaseline value within each study period.
 
• Categories are:                             
 
○ ALT: <math>\leq 1\times</math> ULN, <math>>1</math> to <math><3\times</math> ULN, <math>\geq 3</math> to <math><5\times</math> ULN, <math>\geq 5</math> to <math><10\times</math> ULN, <math>\geq 10</math> to <math><20\times</math> ULN, and <math>\geq 20\times</math> ULN
 
○ AST: <math>\leq 1\times</math> ULN, <math>>1</math> to <math><3\times</math> ULN, <math>\geq 3</math> to <math><5\times</math> ULN, <math>\geq 5</math> to <math><10\times</math> ULN, <math>\geq 10\times</math> to <math><20\times</math> ULN and <math>\geq 20\times</math> ULN
 
○ Total bilirubin: <math>\leq 1\times</math> ULN, <math>>1</math> to <math><1.5\times</math> ULN, <math>\geq 1.5</math> to <math><2\times</math> ULN, <math>\geq 2\times</math> ULN
 
○ ALP: <math>\leq 1\times</math> ULN, <math>>1</math> to <math>\leq 1.5\times</math> ULN, <math>>1.5\times</math> ULN
 
 
 
• With additional categories:                             
 
○ Decreased: postbaseline category <math><</math> baseline category
 
○ Increased: postbaseline category <math>></math> baseline category
 
○ Same: postbaseline category = baseline category
 
 
 
	
Fisher’s exact test for Safety Population and summary for IR Population: Shifts from maximum baseline to maximum postbaseline category

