	
Elevated hepatic criteria: maximum ALT <math>\geq 3\times</math> ULN and maximum total bilirubin <math>\geq 2\times</math> ULN using Performing Lab Reference Ranges. Listing of patients who meet any of the following criteria:
 
 
• Elevated hepatic criteria: defined as maximum ALT <math>\geq 3\times</math> ULN and maximum total bilirubin <math>\geq 2\times</math> ULN
 
• An ALT or AST <math>\geq 3\times</math> ULN
 
• An alkaline phosphatase (ALP) <math>\geq 1.5\times</math> ULN
 
• A total bilirubin <math>\geq 2\times</math> ULN
 
 
The listing will include: patient demographics, concomitant medications, ALT/AST/ALP/total
	
Fisher’s exact test for Safety Population and summary for IR Population: Elevated hepatic criteria Listing: Elevations in hepatic laboratory tests

Special Safety Topic	Definition / Derivation	Analysis / Summary / Listing
	bilirubin/GGT by visit, treatment start and stop dates, and reason for treatment discontinuation. Evaluation of Drug-Induced Serious Hepatotoxicity (eDISH) plot: use maximum ALT measurement and maximum total bilirubin measurement with patients having at least 1 postbaseline ALT and total bilirubin, which contributes 1 point to the plot. The measurements do not need to be taken at the same blood draw.	for Safety Population and IR Population: eDISH plot (to be prepared in Spotfire)
Cytopenias	Cytopenias are defined using the PTs from the following 2 sub-SMQs of the Haematopoietic cytopenias SMQ (20000027) as specified in MedDRA: 
 
• Broad and narrow terms in the Haematopoietic leukopenia (20000030)
 
• Broad and narrow terms in the Haematopoietic thrombocytopenia (20000031)
 
	Fisher’s exact test for Safety Population and summary for IR Population: TEAE by PT within sub-SMQ  Listing: TEAE(to be prepared in Spotfire)

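### The SAP's only combined transaminase-bilirubin category and its eDISH plot use ALT alone, so no by-arm output counts a patient with AST at least 3x ULN, ALT below 3x ULN and bilirubin at least 2x ULN

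*SAP*

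**What the plan says.** The analysis definitions are in SAP Section 6.13.3.1, Table RHBX.6.8, under Hepatic.

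- **Combined category.** The entry opens "Elevated hepatic criteria: maximum ALT", and the listing criteria repeat the definition: "Elevated hepatic criteria: defined as maximum ALT" at least 3x ULN, together with maximum total bilirubin at least 2x ULN. The category gets a Fisher's exact test in the Safety Population and a summary in the IR Population.
- **eDISH plot.** The instruction is to "use maximum ALT measurement and maximum total bilirubin measurement with patients having at least 1 postbaseline ALT and total bilirubin". Each patient contributes one point, and the two maxima need not come from the same blood draw.
- **Elevation table.** "Alanine aminotransferase (ALT) or aspartate aminotransferase (AST): maximum postbaseline measurement" is tabulated at 3x, 5x, 10x and 20x ULN, with the same baseline subsets for both enzymes. Total bilirubin is tabulated separately at 1.5x and 2x ULN.
- **Shift table.** "Shift for ALT, AST, and total bilirubin from maximum baseline to maximum postbaseline will be produced", with identical categories for ALT and AST.
- **By-patient listing.** It takes patients who meet the combined category, and also anyone with ALT or AST at least 3x ULN, alkaline phosphatase at least 1.5x ULN, or bilirubin at least 2x ULN. It prints ALT, AST, alkaline phosphatase, bilirubin and GGT by visit.

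Two protocol rules bear on this.

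- Section 7.1.1, item [1], names when stopping investigational product should be considered, after consultation with the medical monitor. One condition is "ALT or AST >3X ULN and total bilirubin level >2 times ULN or prothrombin time >1.5 times ULN".
- Section 8.4.10 sets the trigger for hepatic monitoring. It begins "If a study patient experiences elevated ALT" at 3x ULN and adds alkaline phosphatase or bilirubin at 2x ULN, each sufficient alone. AST is not named.

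**The concern.** The SAP treats the two transaminases as equals when each is reported alone, and again when it selects patients for the listing. It drops AST only where a transaminase is joined with bilirubin. Neither document gives a reason. The protocol's hepatic event of special interest (Section 8.2.2) names AST beside ALT, and its own combined rule accepts either enzyme.

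The combined category exists to show, by arm, whether both elevations occurred in the same patient. The single-analyte tables cannot show that: one patient in the AST row and one in the bilirubin row may be one person or two. So the combined row could read zero in an arm where a patient had AST at least 3x ULN with bilirubin at least 2x ULN. A reader working from the summary tables would not see the co-occurrence without going to the by-patient listing.

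**Working it through.** No sample size, alpha or event count enters, so there is no planned figure to reproduce. The check applies the definitions to four invented patients.

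**Rules** (values are multiples of ULN; TB is total bilirubin)

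- SAP combined row: max ALT ≥ 3 and max TB ≥ 2.
- eDISH region: the SAP states no reference lines, so I assume those of the combined row, ALT ≥ 3 and TB ≥ 2.
- SAP AST elevation row: max AST ≥ 3.
- SAP listing: ALT ≥ 3, or AST ≥ 3, or TB ≥ 2. The alkaline phosphatase condition is not needed here.
- Protocol 7.1.1 [1]: (ALT > 3 or AST > 3) and TB > 2. The prothrombin alternative is set aside by assuming prothrombin time is not raised.
- Added row: (ALT ≥ 3 or AST ≥ 3) and TB ≥ 2.

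| Invented patient | ALT | AST | TB | SAP combined row | In eDISH region | AST row | Listing | Protocol 7.1.1 [1] | Added row |
|---|---|---|---|---|---|---|---|---|---|
| AST only | 2 | 4 | 2.5 | no | no (point plotted) | yes | yes | met | yes |
| ALT only | 4 | 2 | 2.5 | yes | yes | no | yes | met | yes |
| Both | 4 | 4 | 2.5 | yes | yes | yes | yes | met | yes |
| AST, normal TB | 2 | 4 | 1 | no | no (point plotted) | yes | yes | not met | no |

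Only the first patient changes status. For that patient the combined row tests 2 ≥ 3 and fails, while the added row tests 4 ≥ 3 and 2.5 ≥ 2 and passes. Any patient whose ALT reaches 3x ULN is handled identically by both rows. A raised AST with normal bilirubin stays out of both.

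**Where the first patient is visible under the current SAP.** The AST elevation row at 3x, the bilirubin row at 2x, the AST and bilirubin shift tables, the listing, and an eDISH point at (ALT 2, TB 2.5). None of the by-arm tables joins the two elevations.

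**What the test would show.** Take one case across two arms of the planned 100. The only two possible tables each have probability 100/200 = 0.5, so the two-sided Fisher p-value is 0.5 + 0.5 = 1.0. Adding a case changes the count, not the statistical finding.

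**The case against.** The strongest reply is that nothing is hidden. The SAP already puts this patient in two tested single-analyte tables, in the shift tables, on the plot and in a listing that selects on AST and shows both analytes by visit. A rare liver case is judged from that patient record, not from a Fisher test. This stands. A reader might infer that the case would surface only in the listing; the elevation and shift tables show otherwise.

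A second reply is that there is no conflict with the protocol. A reader might infer that the SAP breaches the protocol's combined criterion. It does not. Section 7.1.1 [1] is a rule for considering discontinuation, not an analysis definition. It uses strict inequalities where the SAP uses at least, and it accepts prothrombin time as an alternative to bilirubin. A patient who met it through prothrombin time with bilirubin below 2x ULN would be outside the added row too, so the fix does not and need not mirror that rule. The protocol comparison supports consistency only. The ALT-only trigger in Section 8.4.10 also shows that leading with ALT is not foreign to the protocol, although it is a single-analyte trigger and says nothing about a combined category.

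Third, ALT alone may be a deliberate choice for specificity, since AST also rises from muscle, and the SAP's special-topic definitions were aligned with the program safety analysis plan (PSAP), which is not among the documents. That is a fair reason to keep the ALT-only row. It is not a reason to have no row that includes AST, and the SAP does not state it.

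**Conclusion.** The point holds as a gap in one summary row and one plot. The SAP's sole by-arm combination of transaminase and bilirubin omits AST, out of step with its own handling of AST in the elevation table, the shift table and the listing, and without a stated reason. The patients affected are those with AST at least 3x ULN, maximum ALT below 3x ULN and maximum bilirubin at least 2x ULN. Each moves the combined count by one.

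How many there would be cannot be computed: neither document gives a rate, and there may be none. A reader might infer that one such case would change the trial's safety conclusion. The documents give this row no decision status, and one case would not produce a significant comparison. The value of the change is that the case becomes visible by arm. It is a low-cost improvement to safety reporting. It does not affect the validity of the trial or any efficacy result.

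The conclusion assumes that the eDISH reference lines match the combined category.

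**What to change.** In SAP Table RHBX.6.8:

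1. Keep the ALT-only combined row unchanged.
2. Add a row for (ALT or AST at least 3x ULN) with total bilirubin at least 2x ULN, using maximum postbaseline values, for the Safety and IR Populations.
3. Add an eDISH panel using AST/ULN, or the larger of ALT/ULN and AST/ULN, beside the existing ALT panel.
4. If the sponsor prefers ALT alone, state why.

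All inputs are in the serum chemistry panel (Protocol Appendix 3). The cost is a little programming and a check against the PSAP: SAP Section 6.13.3.1 lets a change to a special safety topic be documented there without amending the study SAP, and the revision history shows these definitions were aligned with it. The downside is that muscle-derived AST may flag a case, so each should be read with CPK, which is already measured. The protocol's discontinuation and monitoring rules are not touched.

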#### **8.2.2. Adverse Events of Special Interest**

The following adverse events of special interest (AESIs) will be used to determine the safety and tolerability of ixekizumab over the range of doses selected for this clinical study.

AESIs for ixekizumab are:

- cytopenias (leukopenia, neutropenia, and thrombocytopenia)
- clinically significant hepatic events and/or significant elevations in liver function test changes/enzyme elevations (ALT, AST, bilirubin, and alkaline phosphatase)
- infections
- injection-site reactions
- allergic reactions/hypersensitivities
- cerebrocardiovascular events
- malignancies
- IBD

- depression.

Sites will provide details on some of these AEs as instructed on the CRF. Investigators will also educate patients and/or caregivers about the symptoms of allergic/hypersensitivity reactions and will provide instructions on dealing with these reactions (see also Section 6.6.1). A blood sample will be collected as soon as possible for any patient who experiences an AE of a potential systemic allergic /hypersensitivity reaction during the study as judged by the investigator.

Data on preferred terms associated with cerebrocardiovascular events (defined as death, cardiac ischemic events including MI and hospitalization for unstable angina, hospitalization for heart failure, serious arrhythmia, resuscitated sudden death, cardiogenic shock, coronary revascularization procedure, stroke/transient ischemic attack, peripheral revascularization procedure, peripheral arterial event, and hospitalization for hypertension) will be collected, and these events and any deaths will be adjudicated by an external clinical events committee (CEC) made up of a chairman, 2 cardiologists, and a neurologist.

Data on suspected IBD, as identified by events possibly indicative of ulcerative colitis and Crohn's disease, will be collected and the events will be adjudicated by an external CEC with expertise in IBD.

The role of external CECs is to adjudicate defined clinical events in a blinded, consistent, and unbiased manner throughout the course of a study. The purpose of the CEC for adjudication of cerebrocardiovascular events and the CEC for adjudication of suspected IBD events is to ensure that all reported events are evaluated uniformly by a single group.

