	
[4] Clear bump 2 mm thick or more Pain (including burning) (Scored 0-3)
 
[0] None [1] Mild [2] Moderate [3] Severe
	
Listing: TEAE including information collected on Injection Site Reaction eCRF page (to be prepared in Spotfire)

Cerebro-cardiovascular Events	
Cerebro-cardiovascular events will be externally adjudicated by the Central Events Committee (CEC) at the Cleveland Clinic, as outlined in the Manual of Operations. The CEC will adjudicate investigator-reported events selected for adjudication and render an assessment as to whether the event represents a confirmed event (meeting the event definition with all necessary documentation), a non-event (does not meet the event definition and likely represents an alternative or nonevent diagnosis), or lacks sufficient documentation for confirmation of an event. All events which qualify for CEC adjudication will be used for the analysis of cerebro-cardiovascular events. The categories and subcategories of adjudicated events used for the analysis will include the following:
 
 
• Cardiovascular 
 
○ Death (Cardiovascular)
 
○ Cardiac Ischemic Event: Myocardial Infarction and Hospitalization for Unstable Angina
 
○ Serious Arrhythmia
 
○ Hospitalization for Heart Failure
 
○ Hospitalization for Hypertension
 
○ Resuscitated Sudden Death
 
○ Cardiogenic Shock
 
○ Coronary Revascularization
 
 
 
• Neurologic 
 
○ Cerebrovascular Event: Transient Ischemic Attack or Stroke (Hemorrhagic, Ischemic and Undetermined)
 
 
 
• Peripheral Vascular Events 
 
○ Peripheral Arterial Event
 
○ Peripheral Revascularization
 
 
 
 
Events will be analyzed using MedDRA PT nested within the CEC assessment (confirmed event, no event, or insufficient documentation for event determination) and the subcategory. Subtypes of stroke (Hemorrhagic Stroke, Ischemic Stroke, and Undetermined Stroke Type) will be displayed in the analyses nested within Cerebrovascular Event. Subtypes of Serious Arrhythmia (Atrial Arrhythmia, Ventricular Arrhythmia, Heart
	
Fisher’s exact test for Safety Population and summary for IR Population: TEAE by PT within Subcategory Listing: TEAE (to be prepared in Spotfire)

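### Suspected IBD is adjudicated by a blinded external committee, but neither protocol 9.5 nor the visible SAP uses the verdict: IBD is classified by MedDRA preferred term alone.

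*SAP*

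**What the plan says.** **Protocol 8.2.2** names IBD as an adverse event of special interest (AESI). Data on suspected IBD "will be collected and the events will be adjudicated by an external CEC with expertise in IBD". On the external committees generally: "The role of external CECs is to adjudicate defined clinical events in a blinded, consistent, and unbiased manner". The stated purpose, given jointly for the cerebrocardiovascular and the IBD committee, "is to ensure that all reported events are evaluated uniformly by a single group".

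**SAP Table RHBX.6.8, IBD row:** "IBD will be identified using the following subcategory and MedDRA PTs. The narrow terms are considered IBD". There are five narrow terms: inflammatory bowel disease, Crohn's disease, acute haemorrhagic ulcerative colitis, colitis ulcerative and proctitis ulcerative. Nonspecific (broad) terms are referred to Appendix 10. The row plans Fisher's exact tests by preferred term for Period 2 and for Week 0 to 16, a summary for the inadequate responder (IR) population, and a listing. It adds: "Number and percentage of patients, as well as the exposure-adjusted incidence rates will be presented for the Safety Population and IR Population in Period 2". It mentions no committee, verdict or adjudication form.

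**SAP Table RHBX.6.8, cerebro-cardiovascular row:** "All events which qualify for CEC adjudication will be used for the analysis of cerebro-cardiovascular events", and "Events will be analyzed using MedDRA PT nested within the CEC assessment". The assessment categories there are confirmed event, no event and insufficient documentation. The MACE row is built from the adjudication eCRF pages.

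**SAP 6.13.3.1** asks for narrow and broad AESI summaries, where broad pools both sets of terms. If the terms or the analysis of a special safety topic change, the PSAP records the change and overrides the SAP without an amendment.

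**The concern.** The trial convenes an expert committee to decide which suspected events are IBD. The analysis then classifies them by the coded term of the site's report. The two classifications can disagree in either direction, and nothing in the visible plan says which one describes the drug's IBD risk, or that both will be shown.

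This matters more for IBD than for a minor safety topic. IBD is one of only four AESIs that SAP 6.13.3.1 selects for extra Week 0 to 16 summaries and exposure-adjusted rates. The note to exclusion criterion 12 also admits patients with a history of IBD who have had no exacerbation for at least 6 months, so separating IBD from nonspecific bowel events is a practical question in this population. If the choice between the two counts is left open, it will be made after the data are unblinded.

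**Working it through.** The plan states no IBD rate, event count or power, so there is no figure to reproduce. The check is a comparison of provisions, followed by simple scale arithmetic.

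**1. Where each document uses adjudication**

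| Place | Cerebro-cardiovascular | IBD |
|---|---|---|
| Protocol 8.2.2 (collection) | External CEC | External CEC |
| Protocol 9.5 (analysis) | Adjudicated events named | Adjudication not named |
| Protocol 9.5.1 (finding potential AESIs) | Standardized query or sponsor term list | Same |
| SAP Table RHBX.6.8 | Preferred term nested within CEC assessment | Preferred term only |

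In the visible SAP text, adjudication appears only for cerebro-cardiovascular events and MACE.

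**2. What the preferred-term rule does with each combination**

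| Site's coded term | CEC verdict | Narrow count | Pooled broad count |
|---|---|---|---|
| Narrow | Confirmed | Yes | Yes |
| Narrow | Refuted | Yes | Yes |
| Nonspecific, on the broad list | Confirmed | No | Yes |
| Nonspecific, on the broad list | Refuted | No | Yes |

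The narrow count includes refuted narrow-term cases and misses confirmed nonspecific ones. The broad count includes every listed event whatever the verdict. Neither equals the adjudicated count, and showing both does not recover it. A confirmed event whose term is on neither list appears in neither count.

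**3. Scale**

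Input: 100 patients per group (Protocol 9.1, SAP 5.2), hence 200 on ixekizumab.

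- One discordant case in one group: 1/100 = 1.0 percentage point.
- One discordant case in pooled ixekizumab: 1/200 = 0.5 percentage point.

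**4. Would one case change a test?**

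The counts are assumed, because the documents give none. Two-sided Fisher's exact p-values for 2, 3 and 4 ixekizumab cases:

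| Comparison | Placebo cases | 2 cases | 3 cases | 4 cases |
|---|---|---|---|---|
| Pooled, 200 v 100 | 0 | 0.55 | 0.55 | 0.31 |
| One regimen, 100 v 100 | 0 | 0.50 | 0.25 | 0.12 |
| Pooled, 200 v 100 | 1 | 1.00 | 1.00 | 0.67 |
| One regimen, 100 v 100 | 1 | 1.00 | 0.62 | 0.37 |

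The one-regimen rows match the pairwise comparisons planned in SAP Table RHBX.6.2. Moving one case left or right along any row leaves p above 0.05 throughout. The descriptive rate changes and the test conclusion does not. With 3 cases, one reclassification is a third of the count (1/3 = 33%), but that percentage depends wholly on the assumed 3.

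**The case against.** **The SAP follows the protocol's analysis section.** Protocol 9.5 names only adjudicated cerebrocardiovascular events, and 9.5.1 finds potential AESIs by query or term list. A reader might infer that the SAP departs from a planned adjudicated IBD analysis. The documents do not support that, since 8.2.2 promises adjudication but no table. This part of the objection stands: the gap lies between protocol 8.2.2 and 9.5, and the SAP inherits it. It does not remove the gap, because finding potential cases by preferred term is compatible with classifying them by verdict afterwards.

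**The PSAP may govern this row.** It can supersede the table, and the SAP's revision history says the AESI definitions were aligned with it. It was not available here and could contain an adjudicated IBD analysis. This stands as a limit on what can be claimed. Still, the row as aligned is by preferred term only, and the SAP does not point to the PSAP for adjudicated IBD. Appendix 10 is blacked out, but the row describes it only as a term list.

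**Confirmed nonspecific cases are not lost.** If the term is on the broad list, the case is in the broad summary. This stands, and it rules out the reading that such cases vanish from the IBD output altogether. They are, however, mixed there with events that merely can accompany IBD.

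**The comparator does not restrict to confirmed events.** For cerebro-cardiovascular events, all events qualifying for adjudication are used, nested by verdict. This stands: the precedent supports nesting. Naming CEC-confirmed IBD as the descriptive count is a further recommendation, and its justification is that the choice should precede unblinding. No passage compares the validity of the two classifications.

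**Conclusion.** The point holds as a gap in safety reporting. The protocol has suspected IBD adjudicated blind by an external committee, and neither protocol 9.5 nor the visible SAP states any use of the verdict. The preferred-term rule cannot reproduce it.

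The size is 1.0 percentage point on a group's crude IBD rate per discordant case, or 0.5 in pooled ixekizumab, assuming the planned 100 per group. How many cases will be discordant cannot be derived from the documents, and that some patients with quiescent IBD may enrol does not show that term and verdict would differ.

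A reader might infer that a single misclassified case would overturn the treatment comparison. The documents give no IBD rate to support that, and at the small counts tried above no Fisher result crosses 0.05. Alpha, power and the efficacy endpoints are unaffected.

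Confidence in the gap is high for the text supplied. It is conditional on the PSAP not already closing it.

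**What to change.** In the IBD row of Table RHBX.6.8:

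1. Add a summary by treatment group with preferred term nested within the CEC assessment, on the pattern of the cerebro-cardiovascular row. Do this for Week 0 to 16, for Period 2 (with the exposure-adjusted rate) and for the IR population. Name the IBD committee's verdict categories, which the documents do not give.
2. State before unblinding that CEC-confirmed IBD is the count used to describe IBD risk.
3. Keep the narrow and broad preferred-term tables.
4. Add a by-patient listing of reported against adjudicated diagnosis.

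If the PSAP already contains this, a cross-reference in the row is enough. Otherwise the PSAP should carry the same wording, since it can override the SAP. The cost is SAP text and one extra set of tables. Protocol 8.2.2 already requires the adjudication, so no new data collection is needed.
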